This algorithm differs from that used in Greenberg et al²⁶ by the following modifications, considered relevant for COVID-19 based on expert medical opinion: the inclusion of subjects with a solid malignancy who had radiation therapy or any treatment mix; the separation of subjects with a bone marrow transplant and those with an organ transplant; the inclusion of chronic inflammatory demyelinating polyneuropathy and immune thrombocytopenic purpura in the “rheumatologic or other inflammatory condition” group; the inclusion of sickle cell disease, asplenia, and psoriatic arthritis in the “other immune disorders” group; the addition of subjects with primary immunodeficiencies and those with CKD or ESRD; the requirement that subjects with a hematologic malignancy have evidence of usage of an immunosuppressive medication; the reclassification of subjects with only usage of an immunosuppressive medication; the removal of subjects with usage of only low dose prednisone; and the inclusion of an ad-hoc group of subjects who had taken anti-metabolites. Additionally, the following subcategories will be created: the first 9 subject groups were stratified according to treatment status; organ transplant subjects will be stratified according to time of receipt of the first COVID-19 vaccine dose in relation to the date of transplant; and subjects with hematologic malignancy will be stratified by time of receipt of treatment relative to their 1st vaccine dose.

When categorizing subjects with the different types of IC conditions, all the subject groups will be mutually exclusive. Subjects meeting the criteria for classification into only a single IC group will be classified accordingly into subject groups 1-11. Any subjects meeting the criteria for classification into multiple IC groups will be categorized into the >1 IC condition group (12th subject group).

All subjects will be grouped into an overall study population consisting of subjects identified as having an IC condition or not (i.e., non-IC). Subjects with an IC condition will be further categorized into the specific IC condition groups.

Figure 1: Algorithm to define immunocompromising conditions

Algorithm for case definitions of IC conditions in HealthVerity US claims database

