8.3. Variables

Table 1. Immunocompromising Conditions definition

Variable	Role	Data source(s)	Operational definition
Immunocompromising Conditions	Cohort Definition	HealthVerity Vaccine Data	
Subjects will be categorized into the following 12 mutually exclusive IC groups based on the algorithm detailed in Figure 1:
 
Symptomatic HIV/AIDS, solid malignancy, bone marrow transplant recipients, organ transplant recipients, rheumatologic or other inflammatory conditions, primary immunodeficiencies, other intrinsic immune conditions, chronic kidney disease or end stage renal disease, hematologic malignancy, immunosuppressive treatment only, antimetabolites only, or >1 IC condition.

PFIZER CONFIDENTIAL

Table 1. Immunocompromising Conditions definition

Variable	Role	Data source(s)	Operational definition
			
Subjects falling into more than one of these categories will be categorized as having >1 IC condition.
 
At a minimum, subjects will be required to have one inpatient claim or two outpatient claims on separate days with the IC condition of interest in the baseline period. In cases when >14 days of treatment are required it will be based on the dispensed day supply or distinct days of treatment in the baseline period.
 
The main diagnosis codes to identify IC conditions are presented in ANNEX 1. LIST OF STAND ALONE DOCUMENTS.

Table 2. Vaccination Status definitions

Variable	Role	Data source(s)	Operational definition
Any vaccination	Cohort Definition	HealthVerity Vaccine Data	
Patients with a claim for any vaccine will be considered vaccinated with any vaccine based on the following codes:
 
Pfizer/BioNTech: 91300, 0001A, 0002A, 59267100001, 59267100002, 59267100003
 
Moderna: 91301, 0011A, 0012A, 80777027310, 80777027399, 80777027315, 80777027398
 
Johnson & Johnson: 91303, 0031A, 59676058005, 59676058015
 
Source: https://www.cdc.gov/vaccines/programs/iis/COVID-19-related-codes.html

Fully Vaccinated	Cohort Definition	HealthVerity Vaccine Data	
Patients will be considered fully vaccinated if they meet any of the following definitions:
 
Two claims for Pfizer/BioNTech vaccine on separate days with >14 days of follow-up after the 2nd vaccination date. No claims for any other vaccines are allowed.

PFIZER CONFIDENTIAL

Table 2. Vaccination Status definitions

Variable	Role	Data source(s)	Operational definition

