ANNEX 3. ICD-10 CODE LIST

IC Condition	ICD-10 Code
HIV/AIDS*	B20-B24
Solid malignancy	
Organ/system malignant tumors	C00-C07; C11-C19; C22-C80; Z85
Neuroendocrine tumors	C7A; C7B; D3A
Neoplasms of uncertain behavior	D00-D49
Bone marrow transplant	Z94.81
Organ transplant	
Complications of transplanted organ	T86
Organ transplant status	Z94 except Z94.81; Z98.85
Rheumatologic or other inflammatory condition	
Sarcoidosis	D86
Amyloidosis Not Otherwise Specified (NOS)	E85
Familial Mediterranean fever	E85.0; M04
Amyloidosis Not Elsewhere Classified (NEC)	E85.1; E85.3; E85.8
Multiple sclerosis	G35
Other Central Nervous System (CNS) demyelination	G36; G37.1; G37.3; G37.8; G37.9
Acute infective polyneuritis	G61.0; G61.9
Acute myocarditis	I40
Polyarteritis nodosa and other	M30
Allergic alveolitis/pneumonitis NOS	T78.40; J67.9
Other alveolar pneumonopathy	J84.01; J84.02; J84.09

PFIZER CONFIDENTIAL

IC Condition	ICD-10 Code
Enteritis and colitis	K50-K52
Lupus erythematosus	L93.0; L93.2; M32
Diffuse connective tissue disease	L94; M35.8; M35.9
Arthropathy with infection	M12.9; M01.X0; M02.10
Crystal arthropathies	M11
Rheumatoid arthritis/inflammatory polyarthropathy	M05-M14
Inflammatory spondylopathies	M46
Polymyalgia rheumatica	M31.5; M35.3
Chronic inflammatory demyelinating polyneuropathy	G61.81
Immune thrombocytopenic purpura	D69.3
Primary Immunodeficiency	
X-linked agammaglobulinemia	D80.8
Common variable immunodeficiency	D83.1; D83.2; D83.8; D83.9
Immunoglobulin A (IgA) deficiency	D80.2
Immunoglobulin G (IgG) sub-class deficiency	D80.3
Severe combined immunodeficiency	D81.1
Di George syndrome	D82.1
Wiskott-Aldrich	D82.0
Ataxia telangiectasia	G11.3
Interferon-gamma/Interleukin 12 axis deficiencies	D84.89
Persistent complement, properdin or Factor B deficiency	D84.1
Received eculizumab for >14 days in the baseline period	
Chronic granulomatous disease	D71
Chediak-Higashi	E70.330
Leukocyte adhesion deficiency	D72: Genetic anomalies of leukocytes
Myeloperoxidase deficiency	D72.89: Other specific disorders of White Blood Cells (WBCs)

PFIZER CONFIDENTIAL

IC Condition	ICD-10 Code
Other immune conditions	
Disorders of immune mechanism	D89
Neutropenia	D70
Functional disorders of neutrophils	D71
Genetic anomalies of leukocytes	D72.0
Decreased leukocyte count	D72.81
Leukocyte disease NEC	D72.89
Leukocyte disease NOS	D72.9
Myelofibrosis	D75.81
Blood diseases NEC	D47.4; D75.89; D75.9; D89.2
Blood diseases NOS	D75.9; D75.89
Immunologic findings NEC	R76; R83.4-R87.4; R89.4

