Nonspecific immune findings NEC and NOS	R76; R83.4-R87.4; R89.4
Sickle cell disease	D57
Asplenia	Q89.01
Psoriatic arthritis	L40.52
Kidney condition	
Chronic kidney disease	A18.11; A52.75; B52.0; C64.x; C68.9; D30.0x; D41.0x-D41.2x; D59.3; E08.2x; E09.2x; E10.2x; E10.65; E11.2x; E11.65; E13.2x; E74.8; I12.xx; I13.0; I13.1x; I13.2; K76.7; M10.3x; M32.14; M32.15; N01.x-N08.x; N13.1; N13.1x-N13.39; N14.x; N15.0; N15.8; N15.9; N16; N17.x; N18.1-N18.5; N18.8; N18.9; N19; N25.xx; N26.1; N26.9; O10.4xx; O12.xx; O26.83x; O90.89; Q61.02; Q61.1x-Q61.8; Q26.0-Q26.39; R94.4
End stage renal disease	N18.6 AND on dialysis (any type): Z99.2; Z49; Z9115; Z4931; OR Z4901
On hemodialysis	Any subject with the ESRD codes above and ≥ 1 hemodialysis procedure session during the baseline period identified by at ≥ 1 of the following codes: Z49.31;

IC Condition	ICD-10 Code
	Z49.32; I953; A4680; A4690; A4706- A4709; A4730; A4740; A4750; A4755; A4802; A4870; A4890; A4918; E1520; E1530; E1540; E1550; E1560; E1575; E1580; E1590; E1600; E1610; E1615; E1620; E1625; E1636; G0365; G0392; G0393; G8081; G8082; G8085; S9335; 90935; 90937; 90940; 93990; 36800; 36810; 36815
On peritoneal dialysis	Any subject with the ESRD codes above and ≥ 1 peritoneal dialysis procedure session during the baseline period identified by ≥ 1 of the following codes: Z49.02; 90945; 90947
Hematologic malignancy**	
Lymphatic and hematopoietic tissue malignancy	C81-C83; C88-C96

CNS: central nervous system; ICD-10: International Classification of Diseases, 10th Revision; IgG: Immunoglobulin G, IgA: Immunoglobulin A, NOS: not otherwise specified; NEC: necrotizing enterocolitis; WBCs: White blood cells.

*Excluded asymptomatic HIV code of ICD-10: Z21.

**Required to have usage of an immunosuppressive medication (chemotherapeutic agent, immunomodulator, or systemic corticosteroids) for >14 days anytime during the baseline period.

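### Annex 3 lists some diagnosis codes under two IC groups, so a subject with one such code is reported as having more than one IC condition

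*Combined protocol and SAP*

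**What the plan says.** Section 8.2.1 describes 12 groups that do not overlap: 11 single-condition groups and one for subjects who meet several definitions. The allocation rule is "Any subjects meeting the criteria for classification into multiple IC groups will be categorized into the >1 IC condition group (12th subject group". Table 1 in Section 8.3 repeats it: "Subjects falling into more than one of these categories will be categorized as having >1 IC condition". The minimum evidence for a diagnosis is "one inpatient claim or two outpatient claims on separate days with the IC condition of interest in the baseline period".

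The codes themselves are in Annex 3. Table 1 sends the reader elsewhere: "The main diagnosis codes to identify IC conditions are presented in ANNEX 1. LIST OF STAND ALONE DOCUMENTS". Annex 1 contains only the entry None, so Annex 3 is the only code list in the document.

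Three extracts from Annex 3 show the problem:

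- Primary immunodeficiency includes D71, "D72: Genetic anomalies of leukocytes" and "D72.89: Other specific disorders of White Blood Cells (WBCs". D71, D72.0 and D72.89 are also listed under other immune conditions.
- The blood disease row under other immune conditions reads "D47.4; D75.89; D75.9; D89.2". D47.4 also lies inside the solid malignancy range D00-D49.
- The chronic kidney disease row begins "A18.11; A52.75; B52.0; C64.x; C68.9; D30.0x; D41.0x-D41.2x". From C64.x onward, these codes also lie inside the solid malignancy ranges.

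**The concern.** One diagnosis should not make a subject multi-condition unless the plan says so. Section 6 gives the motive for the study as learning which IC conditions go with reduced VE. Section 8.7 then reports breakthrough incidence for each condition, and VE for each condition and for subjects with more than one. If shared codes are sent to the multi-condition group, that group takes in people with a single diagnosis and five condition groups lose them. A subject whose only qualifying code is D71, printed as chronic granulomatous disease, could never be counted under primary immunodeficiency.

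Two smaller points concern the same definitions. The malignancy ranges in Annex 3 have gaps. The transplant timing strata in Section 8.2.1 run in the opposite direction to the baseline window.

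**Working it through.** **Group count.** Section 8.2.1 gives 8 diagnosis-only groups, 1 diagnosis-and-drug group and 2 drug-only groups: 8 + 1 + 2 = 11. Adding the multi-condition group gives 11 + 1 = 12, the plan's own figure.

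**Shared codes.** The inputs are the Annex 3 lists for the 8 + 1 = 9 groups that use a diagnosis. A stem is counted as shared if it lies within the printed codes or ranges of two groups. Z94.81 is not shared, because the organ transplant row excludes it.

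| Pair of groups | Shared stems | Count |
|---|---|---|
| Solid malignancy and kidney | C64, C68.9, D30.0, D41.0, D41.1, D41.2 | 6 |
| Primary immunodeficiency and other immune | D71, D72.0, D72.89 | 3 |
| Rheumatologic and kidney | M10.3, M32.14, M32.15 | 3 |
| Solid malignancy and other immune | D47.4 | 1 |

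The total is 6 + 3 + 3 + 1 = 13, across 5 of the 9 diagnosis-based groups.

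**Dependence on the D72 entry.** The label printed beside D72 under primary immunodeficiency is the one Annex 3 gives to D72.0 under other immune conditions.

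- Read as D72.0: 13 stems.
- Entry ignored: 13 - 1 = 12.
- Read as the whole D72 category, which adds D72.81 and D72.9: 13 + 2 = 15.

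If the three M codes are intended as two conditions, the counts become 13 - 3 = 10, 12 - 3 = 9 and 15 - 3 = 12.

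**One subject followed through the rule.** Take a subject with two outpatient claims on separate days, both coded C64.x, and no other IC code or drug use. The claim threshold is met for solid malignancy, because C64 is in C22-C80. The same two claims meet it for kidney disease, because C64.x is in that row. Two definitions are met, so both statements of the rule require the multi-condition group.

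**Gaps in the malignancy ranges.** Solid malignancy is printed as C00-C07, C11-C19 and C22-C80, which omits C08-C10 and C20-C21. Hematologic malignancy is printed as C81-C83 and C88-C96, which omits C84-C87. No other Annex 3 list contains these positions. A subject coded only in the solid gap, with no other IC code and no qualifying drug use, is classed as non-IC. A subject coded only in C84-C87 cannot enter the hematologic group and falls to a drug-only group if the drug use qualifies there.

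**Transplant strata.** Three places can be set side by side:

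- Section 8.1 puts the baseline period in the 12 months before the first dose, and Table 1 requires the qualifying code within it.
- Section 8.2.1, in describing the eight disease groups, defines both strata by a first dose given before the transplant, at more than or fewer than 100 days. Exactly 100 days is in neither. It covers bone marrow and organ transplant.
- Section 8.2.1, in its list of changes to the algorithm, describes the timing strata for organ transplant only.

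A transplant already on record at the first dose fits neither stratum as worded. The strata could be filled only by a later transplant.

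**The case against.** The plan does deal with overlap. The multi-condition group absorbs anyone who meets two definitions, so the 12 groups remain formally exclusive. A reader might infer that the claim of exclusivity is false. It is not; the fault is that one diagnosis can be counted as two. Section 8.3 also refers to an algorithm in Figure 1, which is not shown in the text available here. A hierarchy in that figure cannot be ruled out, although both written statements of the rule omit one.

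The count depends on convention. It mixes code levels and expands the single printed entry D41.0x-D41.2x into three; counted by printed entry it is 4 + 3 + 3 + 1 = 11. It would also be too strong to call all 13 errors. M32.14 and M32.15 sit inside the lupus range and were placed separately under kidney disease, and M10.3x is listed both as an arthropathy and under kidney disease. Dual membership may be intended for these three. That is a reason to name them as exceptions; it does not help the other stems.

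Section 8.7 plans sensitivity analyses on the IC case definition, and Section 8.9 admits that the accuracy of the modified algorithm is not assessed. Both are relevant, but neither names shared codes, gaps or strata.

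The gaps may be inherited from the source algorithm, and not every skipped position need be a code in use. The share of skipped positions therefore says nothing about how many patients are missed. The transplant wording looks like a drafting slip, and those strata are not among the subgroups listed in Section 8.7. Finally, a reader might infer that every transplant row is labelled as a status or complication code. That is true of the two organ transplant rows. The Z94.81 row is labelled simply as bone marrow transplant.

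**Conclusion.** The rule as written gives a wrong allocation and should be corrected. Between 12 and 15 stems (13 on the most natural reading of D72) place a subject with one qualifying code in the multi-condition group and keep that subject out of every single-condition group. For three of them this may be intended. The conclusion assumes that the written rule governs and that Figure 1 contains no hierarchy.

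The consequence is misallocation within the per-condition incidence and VE outputs, which serve the secondary and exploratory objectives. A reader might infer that the IC versus non-IC comparison is distorted, or that the rates in the remaining groups are biased. The documents support neither inference for shared codes: the subject is IC under either group, and there are no code counts from which to size an effect on any rate.

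The solid malignancy gap is different in kind, because it can move subjects into the non-IC comparator. Its size is also unknown. For the transplant strata, the harm is sub-strata that cannot be used as worded; no reported group result is shown to be distorted.

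**What to change.** **Shared codes.** In Annex 3, assign each code listed twice to one group, mark by name any code meant to give dual membership on its own, and replace D72 with the intended code. Add to Section 8.2.1: *A code listed under two groups counts only toward the group assigned to it in Annex 3, except the codes marked there.* On the 13-stem reading, this leaves no shared stem other than the marked exceptions. Correct Table 1 to cite Annex 3.

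**Code gaps.** Add the codes in use within C08-C10 and C20-C21 to solid malignancy, and those within C84-C87 to hematologic malignancy with its drug requirement kept. Otherwise, state why they are omitted.

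**Transplant strata.** Reconcile Section 8.1 with the two descriptions in Section 8.2.1, so that the order of dose and transplant, the placement of day 100 and the inclusion of bone marrow transplant are each stated once. State how the transplant is dated: the organ transplant rows are labelled status or complication, and the bone marrow row gives a single code without saying whether it dates the transplant. If procedure codes are used, list them in Annex 3.

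**Cost.** Text edits to Annex 3, Section 8.2.1 and Table 1, possibly a short procedure-code list, and a rerun of the cohort code. No new data source is needed. Because Section 8.7 plans rolling updates on monthly data cuts, the correction is best made before further cuts repeat the allocation.

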immune response to the COVID-19 mRNA vaccines in people with an IC condition leads to reduced VE. In the RCTs of the mRNA vaccines, those with an IC condition were largely excluded from the study populations.^{13, 14} A few recently conducted real-world studies that contained subpopulations with IC conditions have found that while the COVID-19 vaccines were effective in this patient group, VE against SARS-CoV-2 infection, symptomatic illness, and COVID-19-related hospitalization was lower than observed in the general populations of these studies.¹⁵⁻²³

On 12 August 2021, the FDA amended the EUA for the mRNA COVID-19 vaccines to allow for the use of an additional dose for certain immunocompromised subjects with moderate to severe IC conditions. According to the Centers for Disease Control and Prevention (CDC) guidelines (COVID-19 Vaccines for Moderately to Severely Immunocompromised People | CDC), the additional dose should be administered at least 28 days following the two-dose regimen of the same vaccine to individuals 18 years of age or older (ages 12 or older for Pfizer-BioNTech) who have undergone solid organ transplantation, or who are diagnosed with conditions that are considered to have an equivalent level of immunocompromise. A third dose of the same Mrna vaccine should be used; however, if the Mrna vaccine product given for the first two doses is not available or is unknown, either Mrna COVID-19 vaccine product may be administered.

Further study of patients with various IC conditions is warranted to gain a better understanding of which IC conditions may predispose people to reduced COVID-19 VE to guide further prevention efforts.

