8.2.1. Inclusion criteria

Patients must meet all of the following inclusion criteria to be eligible for inclusion in the study:

1. Unique enrollees in the HealthVerity Vaccine dataset any time **after** 10 December 2020
2. At least 12 years on the index date (ie, first vaccination date)
3. No evidence of prior COVID-19 infection (a medical claim, pharmacy claim, or chargemaster record with an International Classification of Diseases, 10th Revision, Clinical Modification (ICD-10-CM) diagnosis code of U07.1) in the 12 months prior to the index date
4. Have 12 months of continuous enrollment with medical benefits (with or without pharmacy benefits) prior to the index date

Subjects with an IC condition were identified via an algorithm originally developed and validated by Greenberg et al²⁴ for use in administrative claims database studies. For this study, this algorithm will be modified and expanded based on expert medical opinion. The algorithm is depicted in [Figure 1](#).

Subjects will be identified as immunocompromised if they had ≥ 1 hospitalization or ≥ 2 outpatient visits on separate dates with an ICD-10-CM code on a healthcare claim indicating an IC condition or if they had usage of specific immunosuppressive medications during the 12-month baseline period. The IC case definition will incorporate 8 groups based on clinical diagnoses only, 1 group based on both clinical diagnoses and usage of immunosuppressive medication, and 2 other groups based on usage of immunosuppressive medication only, for a total of 11 groups with an IC condition ([Figure 1](#)). Subjects with >1 IC condition will also be assessed, for a total of 12 mutually exclusive groups for inclusion in this study. The list of ICD-10-CM codes used to identify IC cases by diagnosis and list of immunosuppressive medications are shown in the Annex.

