Eight of the disease groups will include subjects with 1) symptomatic human immunodeficiency virus (HIV)/acquired immunodeficiency syndrome (AIDS); 2) solid malignancy; 3) bone marrow transplant; 4) organ transplant (excluding bone marrow); 5) rheumatologic or other inflammatory condition; 6) a primary immunodeficiency; 7) other immune conditions; and 8) chronic kidney disease (CKD) or end stage renal disease (ESRD). Subjects in these IC groups (shown as “Group 1” in [Figure 1](#)) will be further stratified by treatment status: those with usage of immunosuppressive medications for >14 days anytime during the baseline period and those without any evidence of >14 days of usage of an immunosuppressive medication during the baseline period. Subjects with a bone marrow or

organ transplant will be further stratified by those who received their 1st vaccine dose >100 days prior to their transplant and those who received it <100 days prior to their transplant. Subjects with a solid malignancy will be further stratified by their treatment type: chemotherapy or radiation therapy or immunomodulator, or a mix of these treatments.

The 9th subject group (shown as “Group 2” in [Figure 1](#)) will include those with a hematologic malignancy, required to have usage of an immunosuppressive medication (chemotherapeutic agent, immunomodulator, or systemic corticosteroid) for >14 days anytime during the baseline period; this subject group will be further stratified by their use of an immunosuppressive medication >6 months or ≤ 6 months prior to their index date.

The 10th subject group will include subjects with usage of an immunosuppressive medication (chemotherapeutic agent, immunomodulator, or systemic corticosteroid excluding low-dose [<60mg/day] prednisone) for >14 days anytime during the baseline period, but without any ICD-10-CM diagnosis codes indicating the above listed IC conditions on a healthcare claim anytime during the baseline period. Subjects with >14 days usage of antimetabolites anytime during the baseline period will be excluded from this subject group and placed in the 11th subject group.

[figure not shown]

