8.7. Data analysis

Data analyses will follow extensive feasibility analyses aimed at determining whether a full study and the assessment of vaccine effectiveness are feasible, as illustrated below:

Study implementation approach

Characteristics of the IC, non-IC and total population (IC + non-IC) groups will be described. Descriptive statistics for continuous variables will include N (number of patients), mean, median, standard deviation, Q1, Q3, minimum, and maximum. Categorical variables will be described using frequency counts and percentages.

The incidence rate of breakthrough cases of SARS-CoV-2 infection will be determined based on the following:

- Among fully vaccinated patients, those who have a claim for COVID-19 (ICD-10-CM: U07.1) that occurs on or after >14 days following their second dose of an mRNA vaccine (or 1st dose of Johnson & Johnson) will be considered to have had a breakthrough event. The time from 14 days after the qualifying dose until the breakthrough event will be the person time at risk.

PFIZER CONFIDENTIAL

- Among fully vaccinated patients with no evidence of COVID-19 after their qualifying dose, the time from 14 days after the qualifying dose until the end of follow-up will be the person time at risk.

[figure not shown]
The incidence rate of breakthrough cases of SARS-CoV-2 infection will be calculated as the number of patients who experience the event divided by the observed time at risk, and reported per 100 person years. Poisson 95% confidence intervals will be reported for the incidence rates.

Absolute effect measures such as risk difference between non-IC and IC will be reported. Time period specific effect estimates (eg, at 6 months after vaccination) may be estimated if feasible. The characteristics of the breakthrough infections will be described, including clinical presentation and severity.

The primary analysis will describe results among the non-IC cohort and the IC cohort who are vaccinated with BNT162b2. Subgroup analyses will include results for clinically meaningful subgroups as defined by vaccination type, relevant patient characteristics (eg, age), and each IC condition as listed below:

- HIV/AIDS
- Solid malignancy
- Bone marrow transplant
- Organ transplant (excluding bone marrow)
- Rheumatologic/inflammatory
- Primary Immunodeficiencies
- Other immune condition
- CKD or ESRD
- Hematologic malignancy

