- IS drug use: >14 days IS medications (chemotherapy, immuno-modulators (IM), or corticosteroids excluding low-dose [<60mg/day] prednisone – See Drug List) and not falling into any of the above 9 condition groups
- >14 days of anti-metabolite use and not falling into any of the above 10 condition or drug use groups
- More than 1 IC condition

PFIZER CONFIDENTIAL

Analyses for younger cohorts (eg, 12-15) will also be conducted, as data accumulates.

For the exploratory aim, the Screening Method will be used to calculate VE for the overall study population of subjects with an IC condition and also stratified VE estimates for the different immunocompromised subject groups, with VE also determined for those subjects with >1 IC condition²⁶. We will use the proportion of the population that are vaccinated (PV) and the proportion of subjects with breakthrough SARS-CoV-2 infections that are vaccinated (PCV) to calculate VE using the following formula:

$$VE = (PV - PCV) / [PV(1-PCV)]$$

where PV = the proportion of the population that is vaccinated (ie, vaccination coverage) and PCV = the proportion of subjects with breakthrough SARS-CoV-2 infections that are vaccinated.

Additionally, breakthrough incidence rates and VE will be stratified by age at diagnosis (eg, < 65 and \geq 65 years of age at index vaccination).

Sensitivity analyses will be conducted to test the robustness of findings by varying key study design aspects (eg, continuous enrolment, IC case definition) and data analysis techniques. Other statistical techniques (eg, matched analyses, multiple regression, propensity scores) may be applied on an exploratory basis after careful examination of potential confounders (eg, age, time from vaccination). Exploratory analyses related to alternate dosing may also be conducted upon feasibility results, and as recommendations from public health authorities evolve. The analyses (entirely or in part) will be conducted over time and updated on a rolling basis as monthly data cuts become available.

While the analyses will be focused on the IC population, analyses will also be conducted (in part or entirely) on the non-IC population, the total (IC + non-IC) population or relevant subgroups (eg, other high-risk conditions, vaccination status) to support the interpretation of findings.

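### Condition-specific rates, severity and VE describe patients with that IC condition alone, and no estimate is planned for all patients with the condition

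*Combined protocol and SAP*

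**What the plan says.** Section 8.2.1 defines eleven single-condition groups (8 by diagnosis, 1 by diagnosis plus medication, 2 by medication only) and a twelfth for subjects with several conditions, "for a total of 12 mutually exclusive groups for inclusion in this study". The allocation rule is: "Any subjects meeting the criteria for classification into multiple IC groups will be categorized into the >1 IC condition group (12th subject group". Table 1 in section 8.3 repeats it: "Subjects falling into more than one of these categories will be categorized as having >1 IC condition".

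Treatment alone does not move a diagnosed patient to group 12. Subjects in the eight diagnosis groups "will be further stratified by treatment status: those with usage of immunosuppressive medications for >14 days anytime during the baseline period", or without such use. Hematologic malignancy requires this use. The two medication-only groups are residual in section 8.7: one is for users of immunosuppressive drugs "and not falling into any of the above 9 condition groups", the other for ">14 days of anti-metabolite use and not falling into any of the above 10 condition or drug use groups".

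Section 8.7 reports subgroup results by "relevant patient characteristics (eg, age), and each IC condition as listed below", and the list that follows is the exclusive partition. Screening-method VE is stratified by the same groups, with a separate VE for subjects with more than one IC condition. Section 6 gives the reason for studying individual conditions: to learn "which IC conditions may predispose people to reduced COVID-19 VE".

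**The concern.** A reader will take a row headed organ transplant, or hematologic malignancy, as a statement about people with that condition. Under the allocation rule it is a statement about people with that condition and no other listed IC group.

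The removal may be far from random, because some Annex 3 groups are plausible causes or consequences of others:

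- An organ transplant recipient with qualifying N17 or N18 claims leaves the organ transplant row.
- A bone marrow transplant recipient (Z94.81) with a treated hematologic malignancy (C81-C83 or C88-C96) leaves both rows.
- A patient with a malignancy and qualifying claims for neutropenia (D70) or decreased leukocyte count (D72.81) leaves the malignancy row.

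One hospitalization, or two outpatient visits on separate dates, is enough to qualify for the second group. If many patients move, the named rows become small and selected, and group 12 pools unlike combinations. A rate or VE quoted for a condition could then be applied to patients it does not describe, which bears directly on the purpose given in section 6.

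**Working it through.** The plan states no overlap share, breakthrough rate or VE for subjects with more than one IC condition, so there is no figure to reproduce. The group count is consistent: 8 + 1 + 2 = 11, plus 1 = 12.

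**Rates.** For one condition, let q be the share of person-time in patients who also meet another IC group definition, and k their breakthrough rate divided by that of patients with the condition alone. Both are assumptions. Then

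single-condition rate / all-patient rate = 1 / ((1-q) + qk)

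| q | k | Calculation | Ratio |
|---|---|---|---|
| any | 1.0 | 1/1 | 1.00 |
| 0.3 | 0.8 | 1/(0.7 + 0.24) = 1/0.94 | 1.06 |
| 0.3 | 1.5 | 1/(0.7 + 0.45) = 1/1.15 | 0.87 |
| 0.6 | 1.5 | 1/(0.4 + 0.90) = 1/1.30 | 0.77 |
| 0.8 | 2.0 | 1/(0.2 + 1.60) = 1/1.80 | 0.56 |

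Over q = 0.1 to 0.5 and k = 0.8 to 3.0 the ratio runs from 1.11 (q=0.5, k=0.8) down to 0.50 (q=0.5, k=3.0).

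**Precision.** Events in the single-condition row are a fraction (1-q)/((1-q)+qk) of all events in patients with the condition. The Poisson interval on the log scale is therefore wider by sqrt(((1-q)+qk)/(1-q)):

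- q=0.3, k=1.5: sqrt(1.15/0.7) = 1.28
- q=0.6, k=1.5: sqrt(1.30/0.4) = 1.80
- q=0.8, k=2: sqrt(1.80/0.2) = 3.00

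On the absolute scale the factor is sqrt(ratio/(1-q)), which gives 1.11, 1.39 and 1.67. The simpler factor 1/sqrt(1-q) is right only at k=1.

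**VE.** Assume VE of 0.85 in single-condition patients, q=0.3 and equal vaccine coverage of 0.5 in both sets. The screening formula in section 8.7 then gives, for all patients with the condition:

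- VE 0.70 in patients with a second IC group, equal unvaccinated risk: 1 - (0.7×0.15 + 0.3×0.30) = 0.805. The single-condition row (0.85) is higher.
- VE 0.85 in both, unvaccinated risk doubled in the second set: 1 - (0.7×0.15 + 0.6×0.15)/(0.7 + 0.6) = 0.85. There is no difference, although the breakthrough rate is doubled (k=2).
- VE 0.90 in the second set, equal unvaccinated risk: 1 - (0.7×0.15 + 0.3×0.10) = 0.865. The single-condition row is lower.

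**Can the all-patient result be rebuilt from the planned tables?** No. Group 12 is reported as one pooled row, and no breakdown by combination is specified. Section 8.7 allows sensitivity analyses that vary the IC case definition, but does not say that any of them would be non-exclusive. Section 8.9 does not list the point as a limitation.

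**The case against.** The strongest defence is that the exclusive partition is a legitimate and openly stated choice. Isolating each condition avoids crediting one with the effect of another. In a non-exclusive table a transplant recipient with kidney disease counts in both rows, so neither row isolates its condition. Nobody is lost either: group 12 has its own results, the overall IC versus non-IC comparison is unaffected, and condition-specific results are secondary and VE exploratory in a mainly descriptive study. This stands, and is why the partition should not be replaced.

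Three stronger readings are tempting, and the documents do not support them:

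- A reader might infer that the named rows understate risk. For patients with the condition alone, the rule adds no bias. For all patients with the condition, the direction depends on k, which is not given. Some second-group codes (E11.65, R94.4, the whole of M05-M14) are not obvious markers of deeper immune compromise.
- A reader might infer that the rows exclude patients with the usual complications of the condition. Only a second listed IC group moves a patient. Other comorbidity does not, and treatment and transplant timing are strata within the groups.
- A reader might carry an understated rate over to VE. A higher rate alone leaves VE unchanged, and if patients with several conditions are less well protected, the single-condition VE is overstated.

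The defence does not cover the gap itself. The plan offers no estimate for all patients with a condition, does not label the rows as single-condition, and does not provide what would be needed to derive one from the other.

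**Conclusion.** The point holds as a mismatch of population. Each condition-specific rate, severity summary and VE applies to patients with that IC condition and no other listed IC group, and nothing planned gives the result for everyone with the condition. This follows from the text and needs no assumption.

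The size is not known. In the scenarios worked above with k of 1.5 to 2, the single-condition rate is 0.87 to 0.56 of the all-patient rate. It equals that rate at k=1 and exceeds it if k is below 1. Lower rates in the named rows are plausible but not shown. The loss of precision on the log scale occurs for any q above 0 when patients with a second IC group contribute events.

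The overall IC results are not affected. The change is worth making because the single-condition and all-patient estimates answer different questions, and section 6 gives a reason to want both.

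**What to change.** In sections 8.2.1 and 8.7:

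1. Keep the 12-group exclusive partition and label rows 1 to 9 as condition alone.
2. Beside it, pre-specify for each diagnosis-based condition a non-exclusive breakthrough rate, severity summary and VE, counting each subject in every group whose definition is met.
3. Tabulate the most frequent combinations within group 12, with numbers of subjects, person-time and events.

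This uses data already held and costs a few sentences of text and an extra set of table columns. The downside is that the non-exclusive rows overlap, so they do not add to the total and are not independent of one another; a table footnote should say so.
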